#### **4.7.3        Laboratory Data**

Laboratory data including chemistry, hematology, CSF safety labs (cell counts, protein, glucose) and urinalysis, will be collected throughout the study. A full list of collected laboratory analytes is contained in the protocol (Refer Section 4.5.7 of Protocol v2).

All clinical laboratory data will be stored on the database in the units in which they were reported. Patients' listings and summary statistics at each assessment time will be presented using the International System of Units (SI units; Système International d'Unités). Laboratory data not reported in SI units will be converted to SI units before processing. For most parameters, the measured laboratory test result will be assessed directly using the Roche standard reference range. Certain laboratory parameters will be transformed to Roche's standard reference ranges. A transformation will be performed on certain laboratory tests that lack sufficiently common procedures and have a wide range of Investigator ranges (e.g., enzyme tests that include AST, ALT, and alkaline phosphatase and total bilirubin). Since the standard reference ranges for these parameters have a lower limit of zero, only the upper limits of the ranges will be used in transforming the data. For all laboratory parameters where Roche standard reference range are not applicable, the local laboratory reference ranges will be used.

In the event that the local laboratory does not have laboratory reference ranges, the Roche predefined standard reference range will be used. Laboratory values falling

outside this standard reference range will be labeled "H" for high or "L" for low in patient listings of laboratory data.

In addition to the standard reference range, a marked reference range has been predefined by Roche for each laboratory parameter. The marked reference range is broader than the standard reference range. Values falling outside the marked reference range that also represent a defined change from baseline will be considered marked laboratory abnormalities (i.e., potentially clinically relevant). If a baseline value is not available for a patient, the midpoint of the standard reference range will be used as the patient's baseline value for the purposes of determining marked laboratory abnormalities. Marked laboratory abnormalities will be labeled in the patient listings as "HH" for very high or "LL" for very low.

All abnormal values will be listed.

For selected laboratory parameters descriptive tables will be used to summarize absolute change and percentage change from baseline by visit. For the measurement which are reported as ' $<x$ ' or ' $>x$ ', the value will be replaced by ' $x$ '. For the listing, however, original values as collected in the database will be presented. Values outside the normal ranges will be flagged. Shifts in toxicity grade (where grading is based on numeric ranges within NCI-CTCAE v5) from baseline to the worst grade observed during treatment will be presented.

Spaghetti plots and boxplots for the absolute time course as well the change and percentage change from baseline will be presented for selected parameters.

Additional figures/tables/listings may be produced as deemed appropriate.

For all CSF safety laboratory parameters, in case results have been recorded in duplicate or triplicate, the mean value of the visit's results recorded will be used to produce summary tables and summary plots, while all available values will be shown in the listing and the spaghetti plots.

In addition, the shifts (relative to the normal range) from baseline to the minimum and maximum post-baseline values will be presented. If a subject is missing a baseline value but had a post-baseline value, then the baseline assessment is labeled as "unknown". Likewise, if a subject had a baseline value but had no post-baseline values, then the minimum and maximum are labeled as "unknown". For each parameter, the incidence of shift to low (below the normal range) will be summarized using the minimum post baseline values (across all samples and time points); the incidence of shift to high (above the normal range) will be summarized using the maximum post-baseline values (across all samples and time points).

In case results have been recorded in duplicate or triplicate, for the shift to maximum, the baseline is defined as the highest of the triplicate; similarly, for the shift to minimum, the baseline is defined as the lowest of the triplicate.

Finally, the number of patients with abnormal and marked abnormal absolute values for the CSF safety labs, according to the parameter ranges presented in [Table 4](#), will be summarized by visit.

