4.5.7 Laboratory, Biomarker, and Other Biological Samples

Samples for the following laboratory tests will be sent to the study site's local laboratory or to a central laboratory for analysis:

- Hematology: WBC count, RBC count, hemoglobin, hematocrit *and* platelet count *are required*; differential count (neutrophils, eosinophils, basophils, monocytes, lymphocytes, other cells) *as per local practice*
- Serum chemistry panel: sodium, potassium, chloride, bicarbonate, glucose, BUN or urea, creatinine, total protein, albumin, phosphorus, calcium, total and direct bilirubin, ALP, ALT, AST, uric acid, GGT, CPK, *as per local standard practice*
- Coagulation: INR *and/or* PT, aPTT
- Thyroid panel: thyroid-stimulating hormone
- Viral serology: HBsAg, HCV antibody
- Pregnancy test

All women of childbearing potential will have a serum pregnancy test at screening. Urine pregnancy tests will be performed at specified subsequent visits. If a urine pregnancy test is positive, it must be confirmed by a serum pregnancy test.

- Urinalysis, including dipstick (pH, specific gravity, glucose, protein, ketones, blood) *as per local standard practice* and microscopic examination (sediment, RBCs, WBCs, casts, crystals, epithelial cells, bacteria) *as per local standard practice, if indicated. Microscopic examination is only required in case of an abnormal dipstick result (for example, blood in urine or high protein value).*
- CSF: RBC count, WBC count, glucose, and protein

Samples for the following laboratory tests will be sent to one or several central laboratories for analysis:

- Whole blood sample for determination of CAG repeat length in huntingtin gene (*HTT*) by direct DNA testing, for patient eligibility into the study
- Whole blood sample for clinical genotyping for DNA extraction to enable exploratory analysis and assay development with respect to genes related to *HTT* function and severity of the disease
- CSF samples to perform biomarker analysis, including mHTT and NfL, and other exploratory biomarkers related to HD, neurodegeneration, and inflammation

Samples may also be used to support the development of additional biomarker assays to detect huntingtin protein or other proteins related to HD pathophysiology.

- Plasma samples, which may be used to evaluate biomarkers such as NfL and tau, as well as other exploratory blood-based biomarkers related to HD, neurodegeneration, and inflammation

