#### **4.5.1.1      Mutant Huntingtin protein in CSF**

For CSF mHTT, all statistical modeling will be based on the natural log-transformed parameter. Results on the modelling for the change from baseline will be back-transformed to derive the corresponding percent change in the geometric mean as explained in [Appendix 3](#).

Values below the lower limit of quantitation (BLQ) will be imputed as [The BLQ value]\*0.5. In case a sample has been assessed on more than one date then the value corresponding to the last measurement date will be used.

Descriptive tables and plots as well results from the MMRM model will be provided as described in Section [4.5.1](#) and [Table 2](#).

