**Table 4 CSF Safety Laboratory Ranges**

Parameter	Low	Normal	High	Marked High
Glucose (mmol/L)	<2.2	2.2-3.9	>3.9	>4.4
Protein (g/L)	<0.15	0.15-0.5	>0.5	—
Erythrocytes (cells/ $\mu$ L)	—	0	>0	>5
Leucocytes (cells/ $\mu$ L)	—	0-5	>5	—

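### SAP 4.7.3 drops the operator from censored laboratory results, so the Table 4 counts make every below-limit CSF erythrocyte result High and put some above-limit results one category too mild

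*SAP*

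**What the plan says.** SAP 4.7.3 opens by listing the CSF safety labs (cell counts, protein, glucose) among the laboratory data it covers. After a sentence on descriptive change tables for selected parameters, it deals with results reported as `<x` or `>x`: "the value will be replaced by" x. One exception is stated: "For the listing, however, original values as collected in the database will be presented". Where CSF safety results are recorded in duplicate or triplicate, "the mean value of the visit's results recorded will be used to produce summary tables and summary plots". The section ends by planning to summarise by visit "the number of patients with abnormal and marked abnormal absolute values for the CSF safety labs, according to the parameter ranges presented in" Table 4.

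Table 4 sets these categories:

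- Erythrocytes (cells/µL): Normal 0, High above 0, Marked High above 5.
- Leucocytes (cells/µL): Normal 0 to 5, High above 5.
- Protein (g/L): Low below 0.15, Normal 0.15 to 0.5, High above 0.5.
- Glucose (mmol/L): Low below 2.2, Normal 2.2 to 3.9, High above 3.9, Marked High above 4.4.

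Protocol 4.5.7 says that samples for these tests "will be sent to the study site's local laboratory or to a central laboratory for analysis". Neither document gives a reporting limit for any CSF safety analyte, or a separate rule for putting a censored result into a Table 4 category.

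The biomarkers have a different rule. For mHTT, SAP 4.5.1.1 says "Values below the lower limit of quantitation (BLQ) will be imputed as" half that value, and SAP 4.5.1.2 repeats this for the other CSF and plasma biomarkers.

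**The concern.** Replacing a censored result by its limit is a common convenience for means and plots. It is unsafe for classification when the limit sits on or above a category boundary, because the operator is what tells the reader on which side of the boundary the value lies. Table 4 is exposed because its cut-offs are strict and its normal erythrocyte range is the single value 0. A laboratory that reports no detected cells as `<1` would contribute a High to the table.

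This is a study without study drug, and Protocol 5.2.1 gives lumbar puncture as its example of an invasive protocol procedure. The Table 4 counts are the SAP's dedicated tabulation of CSF safety results. If laboratories report low counts differently, those counts would partly reflect reporting convention rather than findings in the CSF.

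**Working it through.** There is no planned figure to reproduce. The check applies the SAP 4.7.3 rule to censored results, classifies x by Table 4, and compares that with every category the reported result allows. Cell counts are taken as whole numbers. The limits x are assumptions, because the documents give none.

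**Below-limit results**

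| Result | Value used | Category under the rule | Categories the result allows |
|---|---|---|---|
| Erythrocytes `<1` | 1 | High | Normal only (count must be 0) |
| Erythrocytes `<2`, `<3`, `<5` | 2, 3, 5 | High | Normal or High |
| Erythrocytes `<6` | 6 | Marked High | Normal or High (0 to 5) |
| Erythrocytes `<10` | 10 | Marked High | Normal, High or Marked High |
| Leucocytes `<1`, `<3`, `<5` | 1, 3, 5 | Normal | Normal only |
| Leucocytes `<6` | 6 | High | Normal only (0 to 5) |
| Leucocytes `<10` | 10 | High | Normal or High |
| Protein `<0.04` to `<0.14` | 0.04 to 0.14 | Low | Low only |
| Protein `<0.15` | 0.15 | Normal | Low only |
| Protein `<0.20` | 0.20 | Normal | Low or Normal |
| Glucose `<0.1` to `<2.19` | 0.1 to 2.19 | Low | Low only |
| Glucose `<2.2` | 2.2 | Normal | Low only |
| Glucose `<2.5` | 2.5 | Normal | Low or Normal |

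**Above-limit results**

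| Result | Value used | Category under the rule | Categories the result allows |
|---|---|---|---|
| Erythrocytes `>5` | 5 | High | Marked High only |
| Leucocytes `>5` | 5 | Normal | High only |
| Protein `>0.5` | 0.5 | Normal | High only |
| Glucose `>3.9` | 3.9 | Normal | High or Marked High |
| Glucose `>4.4` | 4.4 | High | Marked High only |

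The erythrocyte result is general: x is positive, Normal is 0, so x always exceeds the Normal limit.

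Averaging does not help. If the Table 4 counts use the visit mean, a duplicate of 0 and `<1` becomes (0 + 1)/2 = 0.5, which is High.

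The biomarker rule would not cure it either. Half of 1 is 0.5, so `<1` erythrocytes remains High. It does correct the boundary cases for protein (0.15 × 0.5 = 0.075, Low) and glucose (2.2 × 0.5 = 1.1, Low).

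On size, let f be the share of true zero erythrocyte counts reported as `<x`. Each of these is counted High or Marked High, so the false-abnormal rate among zero counts is f itself: 10%, 30% or 50% if f is 0.1, 0.3 or 0.5. This only restates the assumption, since f is not in the documents.

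**The case against.** The strongest reply concerns scope. The substitution sentence directly follows the one on descriptive change tables, while the CSF-specific rules come later and the Table 4 counts last. It could be read as governing the change tables alone. That reading is possible but less natural: only listings are exempted, the CSF safety labs are within the section, and no other rule covers censored results. Even on the narrow reading, the SAP would not say how to classify them.

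The second reply is that the consequence is small. All analyses are exploratory, Protocol 6.5 plans only limited safety analyses, original values stay in the listings, and no decision rule uses the Table 4 counts. This stands and limits the weight of the point.

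Three stronger readings are tempting, and the documents do not support them:

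- A reader might infer that truly low protein or glucose generally becomes Normal. It does not. A low value reported as a number is unaffected, and a limit below 0.15 g/L or 2.2 mmol/L stays Low. Nothing shows that any laboratory's limit reaches those values.
- A reader might infer that the shift tables are wrong too, and that a false High at baseline hides a later shift. Table 4 is cited only for the by-visit counts. Shifts are described relative to the normal range, and SAP 4.7.3 elsewhere uses the sponsor's standard ranges or local ranges.
- A reader might infer that many patients are misclassified. The documents do not show that any CSF count is reported as censored, or that limits differ between sites; Protocol 4.5.7 only makes this possible.

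**Conclusion.** The point holds for the by-visit Table 4 counts, on the natural reading that the substitution feeds them. A stated rule then gives demonstrably wrong categories. Every below-limit erythrocyte result is counted as abnormal, with certain error for `<1` (High instead of Normal) and `<6` (Marked High, which is impossible). Leucocytes `<6` is wrongly High. Four above-limit results exactly at a cut-off are one category too mild. For protein and glucose, the below-limit error is certain only when the limit equals the lower normal limit; above it the true category is undetermined.

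How many results this affects is unknown, because it depends on reporting limits and censoring frequency that the documents do not give. The primary and secondary analyses are untouched. This is a correction to descriptive safety tables, worth making because it costs so little.

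**What to change.** In SAP 4.7.3, state that CSF safety results are classified for the Table 4 counts from the original result and its operator, and do the same for the shift tables if they use these ranges.

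- Assign a category when every value compatible with the result falls in it. Thus erythrocytes `<1` is Normal, protein `<0.15` and glucose `<2.2` are Low, protein `>0.5` and leucocytes `>5` are High, and glucose `>4.4` and erythrocytes `>5` are Marked High.
- Let `>x` at or above a high or marked-high cut-off take that higher category. Glucose `>3.9` then counts as at least High.
- Otherwise report the result as not determinable, for example erythrocytes `<x` with x of 2 or more, or leucocytes `<10`.
- Keep substitution by x for means and plots only.

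Setting every below-limit cell count to 0 is not a safe shortcut: erythrocytes `<10` would be called Normal although 1 to 9 is High or Marked High.

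The cost is a short SAP paragraph, a minor programming change and a small indeterminate category in the tables. No new data are needed, since original values are already kept for the listings.

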**Table 4 CSF Safety Laboratory Ranges**

Parameter	Low	Normal	High	Marked High
Glucose (mmol/L)	<2.2	2.2-3.9	>3.9	>4.4
Protein (g/L)	<0.15	0.15-0.5	>0.5	—
Erythrocytes (cells/ $\mu$ L)	—	0	>0	>5
Leucocytes (cells/ $\mu$ L)	—	0-5	>5	—

#### **4.7.4 Vital Signs**

Four primary vital signs (pulse/HR, systolic and diastolic BP, body temperature (BT), respiratory rate (RR); all taken in seated position and body weight will be measured at protocol specified visits.

Absolute values and changes from baseline will be summarized with descriptive statistics by treatment arm and study day. Individual vital signs data will be also listed. Spaghetti plots and boxplots for the absolute time course as well the change from baseline will be presented for all parameters.

If the indication of position is missing or measurements are conducted in a different position than seated, the values will be reported in the listing but not used for summary statistics or computation of change.

A listing of subjects meeting any of the abnormality criteria (according to Roche GDSR) outlined in [Table 5](#) will be provided.

**Table 5 Vital Signs Ranges (Seated Position)**

	Low	Normal	High
Pulse/HR (bpm)	<60	60-100	>100
SBP (mmHg)	<90	90-130	>130
DBP (mmHg)	<60	60-80	>80
Temperature (C)	<36.5	36.5-37.5	>37.5
RR (bpm)	<8	8-20	>20

DBP=diastolic blood pressure; HR=heart rate; RR= respiratory rate; SBP= systolic blood pressure.

#### **4.7.5        Electrocardiogram**

Abnormal findings and clinical significance for the finding for ECG parameters will be listed.

#### **4.7.6        Physical/Neurological Examination**

Any abnormality identified at baseline in physical or neurological examination are included in the medical history listing and summary. New or worsened clinically significant abnormalities in physical or neurological examination associated with a study procedure are recorded as AE and therefore reported in AE listings or summaries.

#### **4.7.7        Columbia-Suicide Severity Scale**

The Columbia-Suicide Severity Rating Scale (C-SSRS) is a structured tool to assess suicidal ideation and behavior. Four constructs will be assessed: severity of ideation, intensity of ideation, behavior and lethality of actual suicide attempts. At Screening the “Baseline/Screening version” of the scale is completed. At all subsequent visits (including baseline) the “Since Last Visit version” of the scale is completed.

The C-SSRS collects binary responses to 11 categories: five subtypes of suicidal ideation, five subtypes of suicidal behavior, and self-injurious behavior without suicidal intent. Specifically, the following outcomes are C-SSRS categories and have binary (Yes/No) responses. The categories have been re-ordered from the actual scale to facilitate the definitions of the composite endpoints and to enable clarity in the presentation of the results.

##### **Suicidal Ideation:**

- **Category 1** - Wish to Be Dead
- **Category 2** - Non-specific Active Suicidal Thoughts
- **Category 3** - Active Suicidal Ideation with Any Methods (Not Plan) without Intent to Act
- **Category 4** - Active Suicidal Ideation with Some Intent to Act, without Specific Plan
- **Category 5** - Active Suicidal Ideation with Specific Plan and Intent

##### **Suicidal Behavior:**

- **Category 6** - Preparatory Acts or Behavior
- **Category 7** - Aborted Attempt
- **Category 8** - Interrupted Attempt
- **Category 9** - Actual Attempt (non-fatal)
- **Category 10** - Completed Suicide

##### **Other:**

- **Category 11** - Non-suicidal Self-injurious Behavior

In addition, a numerical score, the Suicidal Ideation Score, will be defined as the highest suicide ideation category (1-5) at which the patient responded "Yes" for the given visit. If the patient did not respond "Yes" to any of these categories, the score will be set to zero.

For each of the aforementioned 11 categories, the number and percent of patients with a "Yes" response at any time post-baseline (regardless of baseline response) will be summarized. Emergent suicidal ideation or behavior will be summarized.

The listed binary categories and the Suicidal Ideation Score will be used to identify a number of composite suicidal endpoints. Note that "recent history" for these composite endpoints is defined as the 12 months prior to Screening and the Screening period. At the Screening visit, CSSRS data is collected for the prior 12 months using the "Baseline/Screening version" of the scale. Therefore, analyses that utilize data from "recent history" will include the historical 12-month data collected at Screening as well as all on-study C-SSRS data collected after enrollment but prior to LP (attempt or successful) using the "Since Last visit version" of the scale. The endpoints are defined as follows:

- **Suicidal Ideation:** A "Yes" answer at any time post first LP (attempt or successful) to any one of the five suicidal ideation questions (Categories 1-5), regardless of the pre-LP responses
- **Suicidal Behavior:** A "Yes" answer at any time after post first LP to any one of the five suicidal behavior questions (Categories 6-10), regardless of the pre-LP responses.
- **Suicidal Ideation or Behavior:** A "Yes" answer at any time post first LP to any one of the ten suicidal ideation or behavior questions (Categories 1-10), regardless of the pre- LP responses.
- **Treatment-Emergent Suicidal Ideation compared to recent history:** A maximum post first LP suicidal ideation score that is increased from the maximum suicidal ideation score in recent history.
- **Treatment-Emergent Serious Suicidal Ideation compared to recent history:** A maximum post first LP suicidal ideation score of 4 or 5 when the maximum suicidal ideation score during recent history was less than 4 (i.e., scores of 0-3). Only patients with a recent history score of 0-3 will be considered evaluable for this outcome.
- **Emergence of Serious Suicidal Ideation compared to recent history:** A maximum post first LP suicidal ideation score of 4 or 5 when the maximum suicidal ideation score during recent history was 0. Only patients with a recent history score of 0 will be considered evaluable for this outcome.
- **Improvement in Suicidal Ideation compared to baseline:** A decrease in the suicidal ideation score at the patient's visit Study Day 85 (3 months), visit Study Day 253 (9 months) and visit Study Day 421 (15 months) C-SSRS assessment compared to the baseline score, defined as the last measurement taken just prior to first LP . Only patients with a baseline score >0 will be considered evaluable for these outcomes.

- **Emergence of Suicidal Behavior compared to all prior history:** The occurrence of suicidal behavior (a "Yes" response to one or more of Categories 6-10) post-LP from not having suicidal behavior prior to LP (includes the "lifetime" score collected at the Screening Visit as well as all C-SSRS assessments collected from the Screening Visit through pre-LP on Study Day 1).

Each of the composite endpoints will be summarized by study day. For each on study emergent outcome listed, only those patients with the specified screening condition will be considered evaluable. In addition, patients who discontinue from the study with no post-LP C-SSRS assessment will be considered unevaluable for analyses of suicidality. Percentages will be based on the number of evaluable patients for each outcome.

In addition, a shift table will be created to demonstrate the change in suicidal ideation score from recent history to post- LP period. The maximum suicidal ideation score in each period will be used to create the shift table. If a patient's recent history suicidal ideation score is missing but has a post-LP score, then the recent history assessment will be labeled as "unknown". Likewise, if a patient's recent history suicidal ideation score is available but has no post-LP score, then the scores during the on-study and post-LP period will be labeled as "unknown".

